6.12 Clinical Management of the Study Patient

As much as possible, the clinical management of each subject will be identical to the standard of care (SOC) at the local institution except as specifically altered by this protocol. Generally speaking the SOC at each institution should be similar to the AHA / ASA published Guidelines for the Management of Aneurysmal Subarachnoid Hemorrhage [Connolly ES et al. *Stroke* 2012;43:1711-1737] and / or the Critical Care Management of Patients following Aneurysmal Subarachnoid Hemorrhage: Recommendations from the Neurocritical Care Society's Multidisciplinary Consensus Conference [Dringier MN et al. *Neurocritic Care* 2011;15:211-240].

6.12.1 Required Clinical Laboratory Testing

Upon admission prior to or during enrollment, the following laboratory blood testing will be recommended: CBC, Comprehensive Metabolic Panel (CMP) to include Sodium, Chloride, Potassium, Bicarbonate, Blood Urea Nitrogen (BUN), Creatinine, Glucose, AST, ALT, Alkaline Phosphatase, PT, International Normalized Ratio (INR), and aPTT as part of the SOC for the treatment of aSAH patients in the acute hospital setting. We recommend a Cardiac Enzyme Panel including Troponin will be drawn on admission prior to or at enrollment and then repeated every 8 hours until a total of 3 sets of cardiac enzymes have been drawn as part of the SOC. In addition, Urinalysis upon admission or prior to enrollment including a urine toxicology screen is recommended as part of the SOC. [Cocaine and other illegal substances can affect the clinical course of aSAH patients].

The following Study related blood work is required above and beyond the SOC upon enrollment: hs-CRP and Anti-Xa levels (Funded by Study).

The following Blood testing will be performed for aSAH patients enrolled in this study from the time of enrollment until stopping of the study drug infusion during the acute hospitalization. Those items that are typically considered the SOC have been labeled as such:

1. CBC: Daily for both treatment groups (SOC)
2. aPTT: Daily for the LDIVH treatment group (Funded by Study). In addition to the enrollment aPTT level, an additional aPTT will be needed on enrollment day #6 for control patients to allow correlation to Anti-Xa values (Funded by Study). Additional aPTT testing for heparin dose adjustments will be performed and will be estimated at 4 samples per LDIVH study patient (Funded by Study). This will mean a total of 18 non-SOC aPTT values will be funded by the study per LDIVH treatment group subject and 2 non-SOC aPTT lab tests will be funded by the study per control group subject.
3. Basic Metabolic Panel: At least every other day for both treatment groups (SOC)
4. hs-CRP: Upon enrollment and enrollment day #2, 4, 6, and 10 (Funded by Study, both treatment groups)
5. Anti-Xa: Upon enrollment and enrollment day #6 (Funded by Study; both treatment groups)

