Peak and Overall Plasma and CSF levels of hsCRP at enrollment and, infusion days #2, 4, 6, and 10 compared between groups.

-SECONDARY CLINICAL EFFECT ENDPOINTS

Trail Making Test Parts A&B at 90 (± 10) days post enrollment.

MoCA at 1-year (± 30 days)

Center for Epidemiologic Studies Depression Scale (CES-D) at 90 (± 10) days post enrollment

Return to work status between groups at 90 (± 10) days

SECONDARY EXPLORATORY PRESPECIFIED BIOMARKER OUTCOMES

Plasma and CSF levels of IL-6, TNF- α , P-Selectin, sICAM-1, HMGB-1, MRP8/14 plasma levels at enrollment and infusion day #2, 4, 6, and 10

ADDITIONAL PRE-SPECIFIED

Rate of MoCA ≤ 20 between groups at the 90-day follow-up visit.

**EXPLORATORY
OUTCOME ANALYSES**

In-hospital incidence of any fever ($> 38.3^{\circ} \text{C}$; $\geq 101.0^{\circ} \text{F}$), Incidence of multiple fever episodes (≥ 3), and Mean Daily Fever Burden.

GCS and NIHSS at enrollment and infusion days # 2,4,6,10, discharge and 90 (± 10) days

MoCA at post-enrollment day #1, 6 and 10

Correlation analysis between MoCA scores and inflammatory biomarker levels with and without adjusting for hemorrhage burden (Hijdra Sum Score).

Incidence of moderate and severe Radiographic Cerebral Vasospasm based on a CTA, MRA, or Catheter DSA obtained between PBD # 6-12 as determined by an independent and blinded core imaging lab.

Incidence of TCD criteria for significant vasospasm (velocities $>200 \text{ cm/s}$ and / or MCA / ICA (Lindgaard) ratio >6)

Incidence of TCD criteria for absence of vasospasm (velocities $<120 \text{ cm/s}$)

Incidence of clinical vasospasm requiring rescue therapy (eg, pressors, endovascular treatment)

Incidence of "Delayed Cerebral Ischemia" defined as:

- Symptoms of neurological deterioration (e.g. hemiparesis, aphasia, decreased level of consciousness)
- Symptoms last for more than an hour
- Symptoms are not explained by other physiological processes (e.g., hydrocephalus, hypotension)

CT or MRI evidence of Vasospasm Related Cerebral Infarction on post-infusion (discharge) imaging as scored by an independent and blinded core imaging lab

Global outcome as measured between group ordinal regression analysis of the modified Rankin Scale score at 90-days and 1-year.
Return to work status between groups at 1-year.
Lawton IADLs at 90 (± 10) days
QOLIBRI-OS at 90 (± 10) days and 1-year.
Checklist Individual Strength-subscale Fatigue (CIS-f) at 90 (± 10) days
Barthel Index at 90 (± 10) days and 1-year

**INVESTIGATIONAL

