6.8 Initiation Of Study Drug, Standard Dose Escalation, And Duration Of Infusion

Once the patient has been randomized, if the patient has been randomized to the LDIVH treatment arm then the study drug will be initiated 12 ± 4 hours following the completion of the aneurysm treatment procedure. The LDIVH infusion will initiate at 8 u/kg/hr. The date and time of study drug initiation will be recorded in the CRF. The control group will not receive any study infusions.

The LDIVH infusion (LDIVH group only) will be initiated at 8 u/kg/hr. This rate of heparin infusion should typically be escalated twice to reach the standard goal infusion rate of 12 u/kg/hr. There should be 12 hours between each dose adjustment. This escalation should result in an increase of the rate by 2u/kg/hr to a minimum target of 12u/kg/hr. A follow-up aPTT should be checked 6 hours after dose initiation and each dose adjustment. The goal rate for the LDIVH group should be **at least** 12 u/kg/hr, however if the aPTT is still below the lower limits of the acceptable range, then 12 hours after the last dose escalation, the rate can be again increased by 1u/kg/hr beyond the minimum of 12 u/kg/hr. (Max infusion rate of 1800 units/hr). Again, LDIVH target is at least 12 u/kg/hr while maintaining an aPTT value within the range that correlates with an Anti-Xa value of 0.1-0.3 u/ml.

Example: Site A initiates LDIVH on Patient X weighing 80kg. Target aPTT for Site A is 40-60 seconds.

LDIVH gtt is initiated at 8 u/kg/hr (640 u/hr) and an aPTT is obtained 6 hours later. aPTT result 6 hours later is 42 seconds. (Even though aPTT was 42, you will always try to get to a minimum of 12 u/kg/hr minimum as long as aPTT is not above the upper goal [60 in this example])

Dose escalation needed.

12 hours after LDIVH initiation, Patient X will have the LDIVH rate increased to 10u/kg/hr (800 u/hr).

aPTT result 6 hours later is 38 seconds

Dose escalation needed.

LDIVH gtt is escalated 12 hours after last dose adjustment (approximately 6 hours after most recent aPTT value) to 12 u/kg/hr (960 u/hr).

aPTT result 6 hours later is 39 seconds

Dose escalation needed.

LDIVH gtt is escalated 12 hours after last escalation (6 hours after aPTT value) to 13u/kg/hr (1040 units/hr)

aPTT result 6 hours later is 42 seconds

No further dose adjustments needed for this patient at this time.

Routine aPTT checked 24 hours later and result is now 36 seconds and Patient X remains at 13u/kg/hr

Dose escalation needed.

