6.9 Study Drug Infusion Safety Monitoring By Investigators

To reduce the risk of bleeding complications in the LDIVH arm of the study, close monitoring of aPTT laboratory values for the LDIVH arm will be done. The aPTT laboratory values for subjects in the LDIVH arm will be collected at regular intervals to monitor anticoagulation effects and adjust the infusion as necessary. aPTT testing will be performed prior to enrollment on all study subjects. aPTT testing will also be done 6 hours after each upwards dose adjustment and at least once daily for the duration of the study drug infusion for patients allocated to the LDIVH treatment group. aPTT testing will occur on control subjects on Infusion day #6 drawn at the same time as the Anti-Xa test listed below.

Anti-Xa testing will occur on patients allocated to both the LDIVH group and the control group at enrollment prior to initiation of the study drug and again on infusion day #6 to help correlate aPTT data between sites. An aPTT value correlating with an anti-Xa value of 0.1 – 0.3 IU/mL is considered within the appropriate target range.

For most hospitals, a CBC (complete blood count) is performed daily for aSAH during admission and the platelet count is inclusive of this test. At a minimum, platelet count will be monitored at least daily for all patients enrolled in the study. We do expect a few cases of type II heparin induced thrombocytopenia within the LDIVH group and/or control group based on the reported incidence of HIT being approximately 0.3-5%. Both the LDIVH group and the control group are at risk for this complication, though we expect the risk to be slightly higher in the LDIVH group. ***We recommend providing a diligent surveillance for this potentially dangerous complication known to be associated with heparin, heparinoid infusions and heparinoid chemical DVT prophylaxis.***

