6.11 Inflammatory Biomarker Collection and Processing

hs-CRP blood levels will be drawn and processed by each site's clinical laboratory and the results of these tests will be documented in the database CRFs for each time point which will include time of enrollment, and post-enrollment days #2, 4, 6, and 10. As such, these values will be immediately available to the DSMB and Steering Committee during the interim analysis.

hs-CRP levels will be measured in the CSF as well. CSF will be sent to the local institution's lab for analysis of hs-CRP in the appropriate tube per the lab's standard procedure.

Additional blood and CSF (when a drain is present) will be drawn at enrollment and post-enrollment days # 2, 4, 6 and 10. The blood and CSF will be processed and stored locally and then shipped to the biomarker core lab for further planned biomarker analysis to be processed in a batch fashion after all samples have been collected. Currently the planned biomarkers to be analyzed include: IL-6, TNF- α , P-Selectin, ICAM-1, HMGB-1, and MRP 8/14.

Biomarker processing kits will be mailed to each site that will include instructions, transfer pipettes, shipping packaging, specimen box, pre-filled labels, and other supplies necessary to process blood to plasma and store them in the -70°C freezer. Each site will need to supply venipuncture supplies (needles, vacutainer tubes, or butterfly needles). Each site will also need to supply their own centrifuge, ice bucket, dry ice, and -70°C freezer space.

Collection of Biomarker Blood Specimens and Processing to Plasma:

1. **Collect 9-10 ml of venous blood** using a lavender top Vacutainer (EDTA). Mix according to standard guidelines. If collecting blood from an IV, PICC, or other line, make sure there are no medications hooked up to the line (such as heparin), if there are, temporarily turn off these infusions and waste at least 5 cc of blood prior to collecting the specimen. Turn infusions back on at the same rate following the blood draw.
2. **Within 30 minutes of the blood draw, centrifuge the tube for 10 min at 500g** (approx. 2,000 rpm in a standard centrifuge). If samples cannot be processed within 30 minutes, the tubes should be kept on ice until they can be centrifuged (*no more than 2 hours delay*). **Do NOT freeze the whole blood samples!** Heavily hemolysed or lipemic samples are to be avoided.

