Esophageal temperature probes in the lower 1/3 of the esophagus are reasonable core body temperature measuring devices and are acceptable for temperature measurements in this study. However, these are most common in intubated patients, and we expect very few of our enrolled patients to have endotracheal intubation during study drug infusion. On awake, non-intubated patients esophageal temperature probes can still be utilized, but may be uncomfortable to patients.

Newer central venous catheter temperature probes (Alsius/Zoll) may also be utilized. Rectal probes may also be used but tend to be slightly less accurate than urinary and esophageal probes. **If none of these probes are available, then oral temperature probes placed in the sublingual space are acceptable** but proper attention should be given to recent eating, drinking, mouth breathing and proper probe placement to improve accuracy.

Infrared ear thermometry tends to be less accurate and is not recommended for this study. Temporal artery thermometers, skin surface thermometers and axillary thermometers are not allowed for purposes of temperature data collection in this study.

Temperature measurements will be recorded into the medical record while the patient is in the intensive care unit according to each site's SOC, but at least every 4 hours. If there is more than one measurement obtained within a given hour, then the highest measurement obtained during that hour will be utilized as temperature data for this study. The method of temperature monitoring should be recorded.

Temperature logs will be collected for each subject. Missing temperature time points will be assumed to equal the most recent previously recorded temperature. A total daily fever burden will be calculated for the duration of the study drug infusion (Daily Fever Burden = Sum of hourly fever burden over 24 hours; Hourly Fever Burden = Any hourly temperature recording $> 37.0^{\circ}\text{C}$ minus 37°C ; thus hourly temperature readings of 37°C or less will result in a "0, zero" fever burden for that hour).

If the patient is not in the ICU and is having temperature measurements every 4 hours, then the 4-hour temperature burden will be calculated as temperature measured during that 4 hours window (or highest measurement if more than one measure) minus 37°C x 4. The Daily fever burden will then be the sum of the six 4-hour temperature burden calculations.

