6.14 Post-Infusion (Pre-Discharge) Head CT

A post-infusion head CT is required by this protocol. Most centers will perform a head CT during the later phases of the acute admission to evaluate for development of delayed hydrocephalus and / or to obtain a baseline scan prior to discharge. As a result, this scan will be considered part of the SOC and will not be funded by the study. We prefer the timing of this scan to be 12 hours (\pm 12 hrs) after completion of the study drug infusion (or an equivalent time period in the control group) to allow for comparisons to the post-procedure (pre-enrollment) head CT. If the patient's hospital discharge is planned for a time period < 24 hours after the cessation of the study drug infusion, the CT scan should be obtained prior to discharge.

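### Section 6.12.1 ends the study blood draws when the infusion stops, which contradicts the enrollment-day schedule and, if followed, would shorten hs-CRP sampling in the LDIVH arm only

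*Protocol*

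**What the plan says.** Two sets of statements govern when study samples are taken.

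**Tied to the infusion**
- Protocol 6.12.1 places CBC, aPTT, metabolic panel, hs-CRP and anti-Xa under one sentence that runs "from the time of enrollment until stopping of the study drug infusion during the acute hospitalization".
- The synopsis defines the primary biomarker endpoint as "Peak and Overall Plasma and CSF levels of hsCRP at enrollment and, infusion days #2, 4, 6, and 10 compared between groups".
- Section 6.12.6: "A total daily fever burden will be calculated for the duration of the study drug infusion". Objective 8 in 1.2.2 also places the fever-burden comparison during the LDIVH infusion.
- Section 6.8: "The control group will not receive any study infusions".

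**Tied to enrollment**
- Item 4 of the 6.12.1 list: "hs-CRP: Upon enrollment and enrollment day #2, 4, 6, and 10 (Funded by Study, both treatment groups".
- Section 6.11 sets hs-CRP at "time of enrollment, and post-enrollment days #2, 4, 6, and 10" and gives the other biomarker draws the same days.
- The Schedule of Events (15.1) puts the hsCRP row on enrollment days. That row does not carry footnote C, which marks the LDIVH-only events.
- Later text in 6.12.6 evaluates fever on enrollment days 2, 4, 6 and 10, and as a hospitalization average of up to 21 days.

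Section 9.2 foresees early discontinuation of study drug but does not say whether sampling continues. The study-success definition in the synopsis accepts a significant reduction in inflammatory biomarkers as an alternative to a MoCA benefit, subject to the bleeding condition.

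**The concern.** The event that ends sampling in 6.12.1 can occur early only in the LDIVH arm. The protocol stops the infusion, temporarily or for good, for bleeding, suspected HIT, hypersensitivity, or a need for therapeutic anticoagulation. A site that follows 6.12.1 literally would then stop drawing hs-CRP, while a control patient with the same complication would be sampled to day 10.

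The missingness would be one-sided and linked to complications. For peak hsCRP the direction is fixed: removing draws can lower a patient's maximum or leave it unchanged, never raise it. The error would favor LDIVH on an endpoint that can count toward study success, and a blood sample that was never drawn cannot be recovered at analysis.

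**Working it through.** The protocol has no figure to reproduce here. The check is a comparison of texts, followed by illustrations of size.

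**1. Draws outside the 6.12.1 window after an early stop (LDIVH only)**

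| Infusion stops | hs-CRP draws outside the window |
|---|---|
| between days 2 and 4 | days 4, 6 and 10 |
| between days 4 and 6 (for example day 5) | days 6 and 10 |
| between days 6 and 10 | day 10 |
| after day 10 | none |

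Under item 4, section 6.11 and the Schedule of Events, no draw is lost in any row. Both readings cannot be right.

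**2. Number of draws.** Section 10.1 plans 44 patients per arm, so 44 × 4 = 176 post-baseline hs-CRP draws in the LDIVH arm. If an assumed 20% stop early, 44 × 0.20 = 8.8 patients. The loss is then 8.8 × 3 = 26.4, 8.8 × 2 = 17.6 or 8.8 × 1 = 8.8 draws for the first three rows. At 10% it is 13.2, 8.8 or 4.4; at 30% it is 39.6, 26.4 or 13.2.

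**3. Peak hsCRP with no drug effect (simulation).** Assumptions: 44 per arm, log-hsCRP with SD 1 at each of five draws, one-sided 5% t test.

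- *Stops after day 2, stoppers no sicker, levels highest on day 4, within-patient correlation 0.3 to 0.6.* The LDIVH mean peak falls by about 0.08, 0.15–0.17 and 0.21–0.25 SD at 10%, 20% and 30% stopping. The error rate is 10–11%, 17–22% and 28–36%. With no early stops it is 5%.
- *Stops after day 4, correlation 0.5.* The error rate is about 6–10% across 10–30% stopping, whether stoppers run 0, 0.5 or 1 SD higher.

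The two sets differ mainly because the first removes the day-4 draw, where the assumed profile peaks, and the second keeps it.

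**4. Day-10 mean, if stoppers are sicker.** Let a fraction f of each arm run δ SD higher, and let only LDIVH lose that group's day-10 draw. The bias is −fδ. With f = 0.20 and δ = 1:
- bias = −0.20 SD
- control variance = 1 + 0.20 × 0.80 × 1² = 1.16
- LDIVH patients left = 44 × 0.80 = 35.2
- SE = √(1.16/44 + 1/35.2) = 0.234
- shift = 0.20/0.234 = 0.855 SE
- one-sided error = P(Z > 1.645 − 0.855) ≈ 21%

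The same steps give about 12% at f = 0.10 and 34% at f = 0.30. With a two-sided 5% test and f = 0.20, false reductions run at P(Z > 1.96 − 0.855) ≈ 13% against a nominal 2.5%. Day 10 alone is not the endpoint, so this shows the mechanism only.

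**5. Basis for the 10–30% range.** The protocol quotes bleeding of about 10–20% (8.5), DVT of up to 20% (section 3) and HIT of about 0.3–5% (6.9). None of these is an early-stop rate: many interruptions are temporary, and some stops would come after day 10. They only make the range reasonable to examine.

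**The case against.** The strongest reply is that the specific rules outweigh one introductory clause. Item 4 names the days and both groups, section 6.11 and the Schedule of Events agree, and the schedule marks LDIVH-only events separately. The protocol also uses infusion time as a calendar label for both arms. Section 6.9 schedules a control aPTT by infusion day 6, which 6.12.1 calls enrollment day 6, and sections 6.12.4 and 6.12.5 apply the infusion period to both arms. On that reading infusion days simply means enrollment days.

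This stands as the likelier intention, and it means that a loss of data is not established. It does not resolve the conflict. Item 4 sits under the sentence with the stopping point, so a coordinator can read it as those days while the infusion runs. If controls have a notional infusion period, nothing shortens it for them.

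Stronger readings are tempting, but the documents do not support them:
- *Every early stopper loses days 4, 6 and 10.* That holds only for a stop before day 4.
- *HIT is under-detected in early stoppers.* Section 6.9 says that "platelet count will be monitored at least daily for all patients enrolled in the study", section 3 treats daily CBCs as standard of care for the study, and the CBC row of the schedule runs to day 14. There is a wording conflict with 6.12.1, not a shown gap in detection.
- *CT infarction is biased toward LDIVH.* Section 6.14 requires the scan in everyone, states its timing after infusion completion as a preference, and gives controls an equivalent time. The synopsis and schedule place it at discharge. The day 6–12 window in the synopsis belongs to angiographic vasospasm, not CT infarction.
- *Fever burden must favor LDIVH.* A total over fewer days can only be equal or lower, but a daily mean over fewer days need not be, and 6.12.6 also gives measures that do not depend on the infusion.

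**Conclusion.** The sampling rule contradicts itself and should be corrected. If 6.12.1 is followed literally, LDIVH patients who stop early may lose the hs-CRP draws after the stop, and controls keep theirs. For peak hsCRP this can only favor LDIVH. For the overall level, the direction depends on who stops and on the time course. Fever burden has the same one-arm window and conflicts with the enrollment-day and hospitalization measures in its own section.

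The size is not known. It depends on the early-stop rate, the timing of stops and the hs-CRP levels of stoppers, none of which the protocol gives. The error rates above, roughly 6–36% for peak hsCRP, are illustrative ranges and not estimates for this trial. They also assume a one-sided 5% test, which section 10.1 specifies for MoCA and not for hsCRP. The case for acting rests on the contradiction, the one-sided mechanism, the role of biomarkers in study success, and the fact that missed draws cannot be repaired later.

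**What to change.** 1. In 6.12.1, replace the infusion-stop end point for hs-CRP, biomarker and anti-Xa draws with the enrollment-day schedule in both arms: days 2, 4, 6 and 10 for hs-CRP and biomarkers, day 6 for anti-Xa. State that these draws continue regardless of infusion status while the patient is in hospital and has not withdrawn, and cross-refer from 9.2.
2. In the synopsis, change infusion days to post-enrollment days.
3. In 6.12.6 and objective 8 of 1.2.2, calculate fever burden over the same post-enrollment days in both arms.
4. Reconcile the CBC end point in 6.12.1 with the daily platelet statement in 6.9, and the late-CT timing in 6.14 with the discharge timing in the synopsis and schedule. This point asks only for consistency and proposes no clinical monitoring rule.

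The cost is a wording amendment and a note to sites. The hs-CRP and anti-Xa draws are already funded for both groups, so the extra work is at most a few already planned draws per early stopper. The amendment helps only patients not yet past their sampling days, so it should be made before or early in enrollment.
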